3. DURATION OF THE STUDY

The patients participating in the study had undergone cataract surgery at the Department of Ophthalmology in Neubrandenburg. Thus, the date of the operation is known.

The duration of the observation is dependent on the duration of the postoperative period to the diagnosis of the PCO or until the exclusion of the PCO due to the information provided by the patient or by the treating ophthalmologist for each individual patient. The observation period and thus also the study period therefore varies with each patient.

The period for data collection started with the first implantation of the intraocular lens L313 in September 2008 and is scheduled to end in December 2016.

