4.2 Patients recruitment

For statistical evaluation, the number of cases is determined using the following formula * before patient recruitment.

$$n = 16 \times \frac{\delta^2}{d^2}$$

n=Subjects number
δ=Standard deviation
d= relevant difference

$$n = 16 \times \frac{0,492^{2**}}{0,1^2} = 387,88 \approx 388 \text{ Patients}$$

80% of the patients eligible for the study underwent surgery 3 to 5 years ago. At a follow-up period of 3 to 4 years, the response rate is 13.9% ***.

This results in:

$$n = \frac{388}{0,139} = 2.791,37 \approx 2.792 \text{ Patients}$$

Due to the relatively high average age (at the time of the operation) of 74.73 years, an even lower response rate is to be expected. For this reason, up to 3000 patients will be contacted.

The patient receives the patient's study information sheet, the declaration of consent as well as an informative sheet for the patients regarding PCO. While retaining one copy of these documents, the patient is required to return the other copy and the completed data collection form to the eye clinic. Only when the signed declaration of consent is present, the patient participates in the study.

*Kutschmann M et al. Aspekte der Fallzahlkalkulation und Powerberechnung anhand von Beispielen aus der rehabilitationswissenschaftlichen Forschung. Rehabilitation 2006;45:377-384

** Zur Vergleichsbasis sind 2 Publikationen mit dem Thema der nachstarquote herangezogen worden:

1. Peterman K, Wildgrube M „A-Konstante und Nachstarquote der Intraokularlinse Akreos™ AO MI-60“, Oktober 2009,
2. Spyridaki M, Höh H „Vergleich von 4 MICS-Intraokularlinsen (ThinLens, AcriSmart, CareFlex, und Acriflex) im Hinblick auf ihre Neodym:YAG-Laser-Kapsulotomieraten“ April 2009

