4.4 Documentation

The data is collected via the Excel program (Version 14.0.7166.5000/32-Bit, Microsoft, USA). The intraoperative information is taken from the surgical books and the respective surgical reports. The following data is recorded.

- Operation Date
- Name and address of the patient
- Date of birth
- Which eye (right/left)
- Anesthesia
- Power of the MICS-IOL
- Surgeon
- Intraoperative parameters (Phaco time, Phaco machine, Hardness of the lens, etc.)
- Intraoperative special features/complications

The postoperative documentation is taken from the charts or the questionnaire filled in by the patient. Here, the patient should indicate (if possible with a date) whether a Nd:YAG laser treatment has already been performed on the operated eye. If a patient does not provide clear information due to ignorance, then the respective registered ophthalmologist will be contacted.

In patients without a previously diagnosed or treated PCO (in the hospital or at the ophthalmologist), the information date is documented instead of the laser date. If necessary, the patient will be brought to the hospital once in order to assess the present capsule opacity.

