4.5 Postoperative Examination

Only if the planned number of 388 eyes is not reached by sending a questionnaire to the patients, the patients, who could not provide information because of uncertainty, are brought to the Eye Hospital Neubrandenburg for the assessment of the postoperative PCO. In this case, a proband study insurance and a travel insurance will subsequently be paid.

As part of the study, the following investigations are then carried out:

- a) General and ophthalmological patient's history
 - Questionnaire on general and ophthalmological medication
 - General pre-existing conditions
 - Previous operations
- b) Best corrected visual acuity
 - ETDRS Panel / Snellen Panel: Letters on panels with decreasing size from top to bottom to determine the visual acuity
- c) Slit lamp examination
 - Eye examination with the help of a microscope to observe the eye under high magnification to assess the anterior, middle and posterior structures of the eye
- d) Assessment of posterior capsule (possibly with dilated pupil)

The newly obtained findings are then supplemented in the data collection table.

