5. STATISTICAL ANALYSIS

For data protection reasons, all data of the patient are immediately pseudonymized after collection. The head of the study center ensures that it is no longer possible to draw any conclusions about the respective patient from the data collected.

The data are evaluated with the computer program STATISTICA (Version 10, StatSoft GmbH, Hamburg, Germany) using the Kaplan-Meyer analysis.

The main question is the determination of the PCO rate after implantation of the MICS intraocular lens L-313 under the conditions prevailing in Neubrandenburg.

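### The Kaplan-Meier PCO rate will describe consenting repliers (13.9% or fewer expected), but the plan presents it as the rate for the lens at Neubrandenburg and does not compare repliers with those contacted

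*Combined protocol and SAP*

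**What the plan says.** **Who enters.** Patients are found from the operating-room books and surgical reports (section 4.1), and up to 3000 are to be contacted (section 4.2). Of these, "Only when the signed declaration of consent is present, the patient participates in the study". On the expected yield, section 4.2 states "At a follow-up period of 3 to 4 years, the response rate is 13.9" per cent. Because mean age at operation is 74.73 years, it adds that "an even lower response rate is to be expected".

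**What is estimated.** Section 5 evaluates the data "using the Kaplan-Meyer analysis". The main question is the PCO rate after implantation of this lens "under the conditions prevailing in Neubrandenburg". No section compares repliers with those contacted or plans a sensitivity analysis for non-reply.

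**Unclear replies.** Section 4.4 gives a first step that does not depend on the count: "If a patient does not provide clear information due to ignorance, then the respective registered ophthalmologist will be contacted". For patients with no PCO diagnosed or treated so far, it records the date of the information in place of the laser date. For patients who could not answer, section 4.5 provides an examination "Only if the planned number of 388 eyes is not reached by sending a questionnaire to the patients". Section 2.4 gives a wider trigger (PCO not documented, or status not known), and section 4.4 leaves it to necessity. Section 3 ends observation at diagnosis of PCO or "until the exclusion of the PCO due to the information provided by the patient or by the treating ophthalmologist".

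**The concern.** The question in section 5 is about eyes that received the lens at this centre. The data will come from about one in seven of the patients contacted, or fewer. Kaplan-Meier deals with unequal follow-up among those who enter the analysis; it does not deal with who enters. If patients with PCO or laser treatment reply more often, or less often, than the others, the curve is shifted. The plan's only answer to low reply is a larger mailing, which narrows the interval and leaves such a shift in place. Section 2.1 says the findings may affect further development of the lens, so a reader needs to know whether the rate applies beyond the repliers.

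The second question is whether an eye whose status stays unknown after the ophthalmologist has been asked is handled in the same way whatever the number recruited. Under section 4.5 it may not be.

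**Working it through.** **1. The plan's own figures (section 4.2).** Inputs: SD 0.492, relevant difference 0.1, reply rate 13.9%.
- n = 16 × 0.492² / 0.1² = 387.30, rounded up to 388. The plan prints 387.88 before rounding; the result is the same.
- Contacts: 388 / 0.139 = 2791.37, rounded up to 2792.
- At 3000 contacts: 3000 × 0.139 = 417 repliers. Reaching 388 needs 388 / 3000 = 12.9%.

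Both planned figures reproduce.

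**2. What selective reply could do.** The documents give no PCO rate for this lens and no reply rate by PCO status, so both are assumptions here. One candidate rate comes from reading the SD as binomial: p = 0.5 − √(0.25 − 0.492²) = 0.411. The publications cited for that SD concern other lenses. Rates of 20% and 10% are added for range.

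Let k be the reply probability with PCO divided by that without, and p the rate among repliers. The rate among all contacted is p / (p + k(1 − p)). For example, with p = 0.41 and k = 1.25: 0.41 / (0.41 + 1.25 × 0.59) = 0.357. The half-width is 1.96 × √(p(1 − p)/388), treating eyes as independent.

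| Rate in repliers | k = 0.67 (1/1.5) | k = 0.8 | k = 1.25 | k = 1.5 | 95% half-width, n = 388 |
|---|---|---|---|---|---|
| 41% | 51.0% | 46.5% | 35.7% | 31.7% | 4.9 points |
| 20% | 27.3% | 23.8% | 16.7% | 14.3% | 4.0 points |
| 10% | 14.3% | 12.2% | 8.2% | 6.9% | 3.0 points |

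- The shift equals the half-width at k = 1.23 or 0.82 when p = 41%, and at k = 1.47 or 0.74 when p = 10%.
- A 10-point shift, the relevant difference in section 4.2, needs k of about 1.55 or 0.67 at 41%.
- At 10%, k = 1.25 moves the rate by only 1.8 points, inside the half-width.

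These are simple proportions. A simulated 4-year Kaplan-Meier rate (constant hazard, follow-up uniform over 3 to 5 years, reply depending on PCO status at reply) agreed with the formula to within half a point.

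**3. Why a larger mailing does not help.** Going from 388 to 417 repliers at 41% changes the half-width from 4.9 to 1.96 × √(0.41 × 0.59/417) = 4.7 points. The shift at k = 1.25 stays at 41.0 − 35.7 = 5.3 points, because n does not enter that formula.

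**4. Unresolved eyes.** Let f be the share of consented eyes still unresolved and u the PCO rate among them; both are assumptions. With 41% among resolved eyes, the rate in all consented eyes is (1 − f) × 0.41 + f × u.

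| f | u = 0 | u = 20% | u = 60% | u = 100% |
|---|---|---|---|---|
| 5% | 39.0% | 40.0% | 42.0% | 44.0% |
| 10% | 36.9% | 38.9% | 42.9% | 46.9% |

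With u between 20% and 60%, the change is about 1 point (f = 5%) or 2 points (f = 10%). Only the extreme values of u with f = 10% bring it near the sampling half-width (up to 5.9 points).

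**5. The three examination rules side by side.** Section 2.4: PCO not documented or status not known. Section 4.4: if necessary. Section 4.5: only if 388 eyes are not reached, and only for patients who could not answer. Section 4.5 may be meant to define the other two, but the trigger in section 2.4 is wider than that.

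**The case against.** The strongest reply is that the documents contain no evidence of bias. Section 4.2 links reply to follow-up time and to age. Unequal follow-up is what Kaplan-Meier is built for, so reply that varies with operation date does not by itself bias the curve. Age matters only if PCO risk depends on age, and no section says that it does. Every shift in the first table comes from an assumed ratio. All of this stands: the table shows possible size, not a prediction.

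Nor can the proposed comparison repair the feared harm. Weighting on recorded factors cannot correct reply that depends on PCO itself. Those contacted may also include patients who have died and are excluded under section 2.1.2; they would probably be concentrated at older ages and earlier operation years. This stands too, and it is why weighting is no more than an optional extra below.

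On unresolved eyes, section 4.5 can be read as the specific rule that explains the general wording elsewhere. The ophthalmologist is asked first, and the information date in section 4.4 arguably already censors an eye with no known PCO. A reader might infer from section 3 that unresolved eyes are dropped; the text does not state that. What remains is that the three sections do not say the same thing, and that the information date suits an eye known to be free of diagnosed or treated PCO better than one whose status nobody could establish.

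Consent is required and is not in question.

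**Conclusion.** The concern holds in limited form. The estimate will describe consenting repliers, the plan words it as the rate for the lens at this centre, and nothing planned lets a reader judge the step from one to the other. A reader might go further and infer that the PCO rate will be biased, or biased in a particular direction. The documents do not support that: they give no reply rate by PCO status, and their remarks on follow-up time and age are not evidence of it.

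If reply were related to PCO, ratios of about 1.23 or 0.82 would already match the sampling error at 41%; at 10% it would take about 1.47 or 0.74. These figures rest on assumed PCO rates and on 388 independent eyes.

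The examination trigger is secondary. It is an inconsistency in wording that can let the recruitment count decide whether an unresolved eye enters the curve. The likely effect is small, about 1 to 2 points for 5% to 10% unresolved eyes with 20% to 60% PCO among them. The documents do not show how many such eyes there would be, or that there would be any.

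This is an inexpensive improvement that should be made. It is not a flaw that invalidates the design.

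**What to change.** 1. Report the numbers contacted, replied and consented. Compare repliers with all contacted patients on age, operation year and surgeon, using aggregate data from the surgical books as the ethics approval permits. Note that deaths among non-repliers may be unknown.
2. In section 5, word the conclusion as applying to repliers. A curve weighted for recorded factors such as age and surgeon may be added beside the unweighted main curve as an optional sensitivity analysis, with the statement that it cannot correct reply that depends on PCO.
3. Reconcile sections 2.4, 4.4 and 4.5 on when the examination is done, and state that inclusion in the analysis does not depend on reaching 388. Which examination rule applies is for the sponsor and the investigator to settle.
4. Use the information date of section 4.4 as the censoring date only for eyes confirmed free of diagnosed or treated PCO. Censor an unresolved eye at its last date documented as free, and count and report eyes without such a date as not evaluable.

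**Cost.** Wording in sections 2.4, 4.4, 4.5 and 5, and one aggregate table from books already used for screening. Use of non-repliers' records, even in aggregate, may need a supplement to the approval, which section 6 foresees. Reconciling the examination rule could change the number of examinations. Censoring unresolved eyes assumes that their later PCO risk is like that of the other eyes. If the optional weighted curve is added, its half-width at 41% would be 4.9 × √1.1 to 4.9 × √1.3, or 5.1 to 5.6 points, for an assumed design effect of 1.1 to 1.3.

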4.3 Patients identification

Upon completion of the data collection, each patient / patient eye will be provided with a unique patient identification code. This code is used for study purposes only. During and also after completion of the study, the patient can only be identified by the study doctor or the head of study center.

4.4 Documentation

The data is collected via the Excel program (Version 14.0.7166.5000/32-Bit, Microsoft, USA). The intraoperative information is taken from the surgical books and the respective surgical reports. The following data is recorded.

- Operation Date
- Name and address of the patient
- Date of birth
- Which eye (right/left)
- Anesthesia
- Power of the MICS-IOL
- Surgeon
- Intraoperative parameters (Phaco time, Phaco machine, Hardness of the lens, etc.)
- Intraoperative special features/complications

The postoperative documentation is taken from the charts or the questionnaire filled in by the patient. Here, the patient should indicate (if possible with a date) whether a Nd:YAG laser treatment has already been performed on the operated eye. If a patient does not provide clear information due to ignorance, then the respective registered ophthalmologist will be contacted.

In patients without a previously diagnosed or treated PCO (in the hospital or at the ophthalmologist), the information date is documented instead of the laser date. If necessary, the patient will be brought to the hospital once in order to assess the present capsule opacity.

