2.4 Study-investigation-plan

- intraoperative und postoperative data gathering from the medical records
- Filing a questionnaire to the patients, asking for diagnosis and treatment of PCO (if necessary, a postoperative examination in the Department of Ophthalmology Neubrandenburg in order to determine the PCO, if no PCO was documented or if not known)

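### The plan gives two unreconciled events for its Kaplan-Meier analysis of the PCO rate: section 3 ends observation at PCO diagnosis, while section 4.4 names only the laser date

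*Combined protocol and SAP*

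**What the plan says.** Section 5 names Kaplan-Meier as the method and the PCO rate after implantation of the L-313 as the main question. It gives no event, event date or censoring rule. Section 2.1 adds PCO dynamics to the aim and says the findings may influence further development of the lens.

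The time structure has to be read from two other places.

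- **Section 3:** "The duration of the observation is dependent on the duration of the postoperative period to the diagnosis of the PCO". The endpoint is therefore diagnosis. The alternative endpoint is that PCO has been ruled out, on the patient's or the ophthalmologist's report.
- **Section 4.4:** on the questionnaire, "Here, the patient should indicate (if possible with a date) whether a Nd:YAG laser treatment has already been performed on the operated eye". For patients "without a previously diagnosed or treated PCO (in the hospital or at the ophthalmologist), the information date is documented instead of the laser date". The only event date named is that of the laser.

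Three further provisions bear on the dates. Section 2.4 describes the questionnaire as "asking for diagnosis and treatment of PCO", so diagnosis and treatment are treated as separate facts. Section 4.4 takes postoperative data from charts as well as the questionnaire, and has the patient's ophthalmologist contacted when the patient cannot give clear information. Section 4.5 allows a study examination of uncertain patients if 388 eyes are not reached, with its findings added to the same data table.

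**The concern.** PCO diagnosis and Nd:YAG capsulotomy are different events. Diagnosis comes at or before treatment, and a diagnosed eye need not have been treated by the time information is collected. A Kaplan-Meier curve needs one event, one date for it and one censoring date for every eye. Here one section points to diagnosis, another supplies only a laser date, and the analysis section does not choose.

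The main result depends on that choice. The same records give different curves if a diagnosed, unlasered eye is counted as an event at diagnosis, censored at the information date, or left out because it has no date. Any of these curves could be reported as the PCO rate. If the choice is made after the data are seen, a reader cannot tell whether the figure reflects how often the capsule opacified or how often, and how soon, it was lasered.

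**Working it through.** **The plan's own figure.** Section 4.2 gives n = 16 × SD²/d² with SD 0.492 and d 0.1. That is 16 × 0.492²/0.1² = 387.30, rounded up to 388. The printed 387.88 fits an unrounded SD of about 0.4924, since √(387.88 × 0.01/16) = 0.4924. Then 388/0.139 = 2,791.37, rounded up to 2,792. Both figures reproduce. Neither bears on the event definition.

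**The sections side by side.**

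| Eye | Section 3: observation ends at | Section 4.4: date recorded |
|---|---|---|
| PCO diagnosed, then lasered | diagnosis | laser date, if known |
| PCO diagnosed, not lasered | diagnosis | none named: no laser date, and outside the group given an information date |
| Lasered, date not remembered | diagnosis | charts or ophthalmologist may supply it; no rule if they do not |
| Neither diagnosed nor treated | exclusion of PCO | information date |
| PCO first found at the study examination | diagnosis, i.e. the visit | not stated |

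The sections agree only for eyes with no PCO. In the first row, dating at laser instead of diagnosis moves events later. In the second, censoring the eye removes an event. Leaving the eye out removes both the event and the eye, which lowers the level the curve finally reaches. Both effects pull the same way, so a curve built from section 4.4 alone runs later and lower than a curve of diagnosed PCO.

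**Illustration of scale.** All inputs here are assumptions, because the documents give none of them:

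- time to diagnosis is exponential, with 5-year incidence P of 30% or 40%;
- information dates fall 3 to 5 years after surgery, so nothing is censored before 3 years and the Kaplan-Meier value at 3 years is the cumulative proportion;
- a share s of diagnosed eyes is lasered, after an exponential delay with mean m years.

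Formulas:

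- λ = −ln(1 − P)/5 and μ = 1/m.
- Diagnosis by 3 years: D = 1 − exp(−3λ).
- Laser by 3 years: L = s × [1 − (μ·exp(−3λ) − λ·exp(−3μ))/(μ − λ)]. With no delay, L = s × D.

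For P = 30%:

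- λ = 0.0713 and D = 1 − exp(−0.214) = 19.3%.
- s = 0.8, m = 0.5 (μ = 2): L = 0.8 × 0.163 = 13.0%.
- s = 0.5, m = 1 (μ = 1): L = 0.5 × 0.134 = 6.7%.

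For P = 40%:

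- λ = 0.1022 and D = 26.4%.
- The same two laser settings give 0.8 × 0.224 = 18.0% and 0.5 × 0.186 = 9.3%.

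With s = 1 and no delay, L equals D. In this model the two definitions coincide only if every diagnosed eye is lasered at once. A simulation of the same model agrees to within 0.2 percentage points.

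**The case against.** The strongest reply is that section 3 already supplies an event and a censoring point: diagnosis, or exclusion of PCO. Section 4.4 is a documentation instruction and never says that the laser date is the analysis event. On that view the plan lacks only a cross-reference.

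Much of this stands. A reader might infer that the plan has no event at all, and the documents do not support that, because section 3 implies one. Nor do they support saying that every undated laser is left without remedy, since section 4.4 already plans chart review and contact with the ophthalmologist. PCO first found at the study examination is not undatable either: under section 3 the examination is the diagnosis, and section 4.5 makes it a contingency only. The data collection form might ask for a diagnosis date.

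What does not stand is that this settles the analysis. No section requires a diagnosis date or says how one would be used. The ophthalmologist may supply a missing date, but the plan does not say which date counts. If laser were meant throughout, section 3 would be wrong, and section 4.4 would have no reason to withhold the information date from diagnosed, untreated eyes.

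It is also fair to object that no effect size can be shown. The illustration rests wholly on assumptions and shows only that the definitions can differ materially.

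**Conclusion.** The point holds as a conflict between two stated events that section 5 leaves unresolved. If the data are recorded as section 4.4 is written, lasered eyes are dated at treatment and diagnosed, unlasered eyes have no recorded date. The resulting curve is then later and lower than the PCO rate it is named for.

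The direction follows from the text. The size does not: it depends on the share of diagnosed eyes that are lasered and the delay to laser, and the documents give neither. Under the assumed settings the 3-year estimate is 19.3% for diagnosis against 6.7% to 19.3% for laser (30% 5-year incidence), or 26.4% against 9.3% to 26.4% (40%). A reader might take these ranges as a forecast of bias in this study, and the documents do not support that.

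The conclusion would weaken if the form, which was not available, records diagnosis dates. Section 5 would still have to say how they are used. Because this is the only analysis described and it answers the main question, the rule should be fixed before the data are analysed.

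**What to change.** In sections 3, 4.4 and 5, state one rule:

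- **Event:** the first documented PCO diagnosis or Nd:YAG laser, whichever is earlier.
- **Censoring:** eyes with neither are censored at the information date.
- **Data table:** add columns for PCO diagnosis date and source of date.
- **Label:** clinically diagnosed or treated PCO, with a laser-only curve beside it so that the effect of the definition can be seen.
- **PCO first found at the study examination:** keep it in the main curve as an event at the visit date. Dropping these eyes while censoring eyes found clear at the same visit would be exclusion by outcome and would bias the curve downward.
- **PCO eyes still undated after chart and ophthalmologist enquiry:** keep them as events at the latest possible date, the information date, and state their number.
- **Sensitivity analysis:** one analysis covering these last two groups, either interval-censored or by rerunning Kaplan-Meier with the earliest and then the latest possible dates.

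If diagnosis dates cannot be obtained, make first Nd:YAG capsulotomy the event, censor all other eyes at the information date, and report a capsulotomy rate, not a PCO rate.

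The cost is wording in three sections, two columns, one extra curve and one sensitivity analysis. The label becomes narrower. Diagnosis dates will be incomplete, so some lasered eyes will still be dated at treatment. Placing undated eyes at the latest date lowers the early part of the main curve, which is why the earliest-date bound is needed next to it.

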2. SYNOPSIS

2.1 Aim of the study

This study protocol is designed to collect surgical and postoperative information to determine the PCO rate and PCO dynamics of the MICS L-313 intraocular lens. Depending on the result, these findings may influence the further development of the intraocular lens L-313.

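### If the one-off hospital examination is used and PCO is the event, eyes first found to have PCO there have no known onset date; ordinary Kaplan-Meier at the visit date would understate PCO up to about 4 years

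*Combined protocol and SAP*

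**What the plan says.** Section 2.1 states the aim as "to determine the PCO rate and PCO dynamics of the MICS L-313 intraocular lens", so the time course is an objective alongside the rate. Section 3 makes each eye's observation time "dependent on the duration of the postoperative period to the diagnosis of the PCO or until the exclusion of the PCO".

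Section 4.4 describes one date per eye. This is the date of laser treatment or, for an eye with no PCO diagnosed or treated so far, "the information date is documented instead of the laser date". It then allows a single examination: "If necessary, the patient will be brought to the hospital once in order to assess the present capsule opacity".

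Section 4.5 sets the condition for that visit, "Only if the planned number of 388 eyes is not reached by sending a questionnaire to the patients", and limits it to patients who were unsure of their status. Sections 2.4 and 4.4 mention the visit without the 388-eye condition. Section 4.5 then says "The newly obtained findings are then supplemented in the data collection table". No section states what event date a PCO found at this visit receives.

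Section 4.2 notes that "80% of the patients eligible for the study underwent surgery 3 to 5 years ago". Section 5 gives the whole analysis method as "using the Kaplan-Meyer analysis". Interval censoring, left censoring and sensitivity analyses are not mentioned.

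**The concern.** A single late examination shows whether the capsule is opaque on that day. It does not show when the opacity began. For an eye first found to have PCO there, onset lies between the last documented clear capsule (or surgery, if there is none) and the visit. For most eligible patients that window could cover 3 to 5 years, which is most of the follow-up.

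Kaplan-Meier treats the entered date as the exact event time. If the visit date is entered, the event time is set by when the clinic invited the patient. Events that belong early on the curve are moved late, into a period when the risk set is shrinking. The curve would then suggest PCO that starts slowly and accelerates. Section 2.1 says the results may influence further development of the lens, so an artefact of this kind could matter.

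**Working it through.** **Is the visit likely to be used?**
- Section 4.2: 16 × 0.492² / 0.1² = 387.30. The plan prints 387.88; both round up to 388.
- 388 / 0.139 = 2791.4, rounded up to 2,792, as stated.
- 3000 × 0.139 = 417 replies, a margin of 29 over 388.
- 388 / 3000 = 12.9%. Any usable reply rate below this triggers section 4.5, counting one eye per reply. The plan expects a rate below 13.9%.

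**Assumptions for the size of the bias (none is in the documents).** Constant hazard; true 3-year PCO of 20% or 40%; contact or visit uniform over 3 to 5 years; a random share f of PCO cases found only at the visit and dated then.

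**Up to 3 years.** No eye is censored before 3 years, so Kaplan-Meier estimates (1 − f) × F(t), where F(t) is the true cumulative PCO. The error is −f × F(t). At 3 years:
- f = 10%: 0.10 × 20 = 2 points, and 0.10 × 40 = 4 points, too low.
- f = 25%: 0.25 × 20 = 5 points, and 0.25 × 40 = 10 points, too low.

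**From 3 to 5 years.** Let λ = −ln(1 − F(3))/3, F(t) = 1 − exp(−λt) and G(t) = (5 − t)/2. The share at risk is G(t)·[1 − (1 − f)F(t)]. The event rate is G(t)(1 − f)λ·exp(−λt) + f·F(t)/2. Kaplan-Meier estimates 1 − exp(−integral of event rate / share at risk).

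| Cumulative PCO, % | 2 y | 3 y | 4 y | 4.5 y | 4.9 y |
|---|---|---|---|---|---|
| True (3-year 40%) | 28.9 | 40.0 | 49.4 | 53.5 | 56.6 |
| KM, f = 10% | 26.0 | 36.0 | 47.3 | 54.1 | 63.6 |
| KM, f = 25% | 21.6 | 30.0 | 44.1 | 54.1 | 69.9 |
| True (3-year 20%) | 13.8 | 20.0 | 25.7 | 28.4 | 30.5 |
| KM, f = 10% | 12.4 | 18.0 | 24.7 | 28.9 | 35.1 |
| KM, f = 25% | 10.4 | 15.0 | 23.1 | 29.4 | 40.7 |

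A simulation of 400,000 eyes agrees to within 0.3 points. With f = 0, Kaplan-Meier recovers the truth.

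**Precision.** With 388 eyes, the binomial standard error at 3 years is √(0.20 × 0.80/388) = 2.0 points or √(0.40 × 0.60/388) = 2.5 points. At 4.9 years, 388 × 0.05 × [1 − (1 − f)F(4.9)] leaves about 9 to 15 eyes at risk in the four scenarios.

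**Sensitivity to the visit times.** A second simulation used 388 eyes and 400 replicates, with 80% contacted at 3 to 5 years and the rest spread over an assumed 0.5 to 8 years. At f = 25%:

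| Assumed 5-year PCO | 3 y: KM vs true | 4.9 y: KM vs true |
|---|---|---|
| 20% | 9.5 vs 12.5 | 22.9 vs 19.6 |
| 41% | 20.7 vs 27.1 | 46.0 vs 40.4 |
| 59% | 31.2 vs 41.4 | 64.1 vs 58.3 |

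The direction is the same, with a smaller late overshoot.

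**What f might be.** Suppose the visit only fills the shortfall to 388, one eye per reply, and examined eyes have the same PCO risk as the others. A usable reply rate of 12% gives 360 eyes, 28 short, so f is about 28/388 = 7%. An f of 10% needs a rate of 0.90 × 388/3000 = 11.6%, and an f of 25% needs 0.75 × 388/3000 = 9.7%.

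**The case against.** The strongest reply is that the problem is conditional three times over.

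- **The visit may never happen.** Section 4.5 reserves it for a shortfall, and section 4.4 first sends unclear answers to the treating ophthalmologist. At 13.9% the target is met by questionnaire. This stands as a condition, but the margin is 29 replies and the plan itself expects fewer.
- **The event may be laser treatment.** The date field is a laser date, the questionnaire asks about Nd:YAG treatment, and one comparison source in section 4.2 reports capsulotomy rates. Under that definition an untreated PCO found at the visit is not an event, and ordinary Kaplan-Meier with censoring at the visit is appropriate. A reader might infer that the bias persists under any event definition; it does not. But sections 2.4, 3 and 4.5 speak of diagnosing or assessing PCO, and the plan never defines the event.
- **The visit date is an inference.** A reader might take the plan to have chosen it as the event date. The documents show only that no dating rule exists. The visit date is the natural entry in a table with one date per eye.

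The size is also open to challenge, because f has no basis in the documents. At f = 10% the 3-year error of 2 to 4 points is of the same order as the sampling error. A reader might also expect the curve to be too high throughout years 3 to 5. The table does not support that: it is still low at 4 years and within about 1 point of the truth at 4.5 years.

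Finally, section 5 names the PCO rate as the main question, and intervals running from surgery to 3 to 5 years say little about timing. Both points are fair. However, a PCO rate needs a time point, and the 3-year rate is itself affected.

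**Conclusion.** The point holds conditionally. If the section 4.5 visit is used and PCO is the event, the plan gives no way to handle eyes whose onset is known only to an interval, and Kaplan-Meier at the visit date would bias the curve. The robust effect is understated PCO up to about 4 years. Overstatement is material only close to 5 years, where too few eyes remain for that part of the curve to be relied on anyway.

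The 3-year shortfall is f times the true 3-year PCO in the simple model. At f = 25% and a true 40%, it equals the plan's own relevant difference of 0.1. The hazard shape, PCO levels, visit times and f are all assumed, so the actual bias in this study cannot be computed from the documents. If f is small, so is the bias.

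**What to change.** 1. For each eye with PCO first found at the section 4.5 visit, record two dates: the last documented clear capsule (surgery date if none) and the visit date.
2. In section 5, estimate the PCO curve with an interval-censored (Turnbull) estimator. Enter these eyes as intervals and documented diagnoses as dated events, noting that these are diagnosis dates and not onset dates.
3. Report ordinary Kaplan-Meier separately for time to Nd:YAG laser, with unlasered examined eyes censored at the visit.

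As a check, the Turnbull estimator was run in the simple model above with 388 eyes, f = 25%, 60 replicates and the lower bound set at surgery. It gave 28.6/39.5/56.2% at 2/3/4.9 years against true values of 28.9/40.0/56.6%, and 13.4/19.7/29.7% against 13.8/20.0/30.5%. Sampling SDs were about 2 to 4 points, against about 2 to 5 for Kaplan-Meier.

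The cost is one extra date column, a short addition to section 5, and possibly software other than the named package. Wide intervals contribute little about timing, so the shape of the curve will rest mainly on the dated diagnoses. The last clear-capsule date is best collected when the charts and ophthalmologists are first consulted.
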